**14.3.2 Listing of Deaths, Other Serious and Significant Adverse Events****Table 307: Listing of Serious Adverse Events**

Adverse Event	Associated with Dose No.	No. of Days Post Associated Dose (Duration)	No. of Days Post Dose the Event Became Serious	Reason Reported as an SAE	Severity	Relationship to Study Treatment	If Not Related, Alternative Etiology	Action Taken with Study Treatment	Participant Discontinued Due to AE	Outcome	MedDRA System Organ Class	MedDRA Preferred Term
Participant ID: , Vaccination Arm: , AE Number:												
Comments:												
Participant ID: , Vaccination Arm: , AE Number:												
Comments:												

**Table 308: Listing of Non-Serious, Unsolicited, Moderate or Severe Adverse Events**

Adverse Event	Associated with Dose No.	No. of Days Post Associated Dose (Duration)	Severity	Relationship to Study Treatment	If Not Related, Alternative Etiology	Action Taken with Study Treatment	Participant Discontinued Due to AE	Outcome	MedDRA System Organ Class	MedDRA Preferred Term
Participant ID: , Vaccination Arm: , AE Number:										
Comments:										
Participant ID: , Vaccination Arm: , AE Number:										
Comments:										

**Table 309: Listing of Other Significant Adverse Events**

Adverse Event	Number of Doses Received at Time of Event	No. of Days Post Associated Dose	Duration of Event	Severity	MedDRA System Organ Class	AESI Type	Relationship	Outcome
Participant ID: , Vaccination Arm: , AE Number:								
Comments:								
Participant ID: , Vaccination Arm: , AE Number:								
Comments:								

Implementation Note:

The column AESI Type will contain PIMMC, MAAE, or NOCMC if the AESI is classified as one of those three categories, otherwise it will state the PT of the AESI.

### **14.3.3 Narratives of Deaths, Other Serious and Significant Adverse Events**

(not included in SAP, but this is a placeholder for the CSR)

**14.3.4 Abnormal Laboratory Value Listings (by Participant)****Table 310: Listing of Abnormal Laboratory Results - Chemistry**

Participant ID	Vaccination Arm	Sex	Age (years)	Planned Time Point	Actual Study Day	Laboratory Parameter (Units)	Result (Severity)	Relationship to Study Treatment	If Not Related, Alternate Etiology	Action Taken with Study Treatment	Participant Discontinued Due to Result?

**Table 311: Listing of Abnormal Laboratory Results - Hematology**

Participant ID	Vaccination Arm	Sex	Age (years)	Planned Time Point	Actual Study Day	Laboratory Parameter (Units)	Result (Severity)	Relationship to Study Treatment	If Not Related, Alternate Etiology	Action Taken with Study Treatment	Participant Discontinued Due to Result?

### 14.3.5 Displays of Laboratory Results

#### 14.3.5.1 Chemistry Results

**Table 312: Laboratory Results by Parameter, Maximum Severity, Time Point, and Vaccination Arm – Any Chemistry Parameter**

Time Point	Vaccination Arm	N	None		Mild/ Grade 1 (Low)		Mild/ Grade 1 (High)		Moderate/ Grade 2 (Low)		Moderate/ Grade 2 (High)		Severe/ Grade 3 (Low)		Severe/ Grade 3 (High)		Missing	
			n	%	n	%	n	%	n	%	n	%	n	%	n	%	n	%
Baseline	Group 1: $5 \times 10^{10}$ vp ChAd/ 30 µg SAM-S	x	x	x	x	x	x	x	x	x	x	x	x	x	x	x	x	
	Group 3A: 30 µg SAM-S/ 30 µg SAM-S																	
	Group 3B: 30 µg SAM-S/ 3 µg SAM-S																	
	Group 4: 10 µg SAM-S-TCE/ 3 µg SAM-S-TCE																	
	Group 5: 3 µg SAM-S-TCE																	
	Group 6: 6 µg SAM-S-TCE																	
	Group 9: 3 µg SAM-S-TCE																	
	Group 10: 6 µg SAM-S-TCE																	
	Group 11: 10 µg SAM-S-TCE																	
	Group 13: $5 \times 10^{10}$ vp ChAd-S-TCE																	
	Group 14: $1 \times 10^{11}$ vp ChAd-S-TCE																	
	Group 15: $5 \times 10^{11}$ vp ChAd-S-TCE																	
All Participants																		

Time Point	Vaccination Arm	N	None		Mild/ Grade 1 (Low)		Mild/ Grade 1 (High)		Moderate/ Grade 2 (Low)		Moderate/ Grade 2 (High)		Severe/ Grade 3 (Low)		Severe/ Grade 3 (High)		Missing	
			n	%	n	%	n	%	n	%	n	%	n	%	n	%	n	%
Day 8	...																	
Day 29 (pre-dose 2 for Groups 1 and 3A)	...																	
Day 36 (8 days post-dose 2 for Groups 3A and 4)																		
Day 85 (pre-dose 2 for Groups 3B and 4)	...																	
Day 92 (8 days post-dose 2 for Groups 3B and 4)																		
Max Severity Post-Baseline	...																	

Note: The “Maximum Post Baseline” rows indicate the maximum severity experienced by each participant at any time point post baseline, including unscheduled assessments.  
N = Number of participants in safety population

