#### Clinical Laboratory Assessments

Clinical safety laboratory parameters evaluated after receipt of study product will include white blood cells (WBC), hemoglobin (HgB), platelets (PLT), alanine aminotransferase (ALT), aspartate aminotransferase (AST), alkaline phosphatase (ALP), total bilirubin (T Bili), creatine kinase (CK), and creatinine (Cr). These evaluations will be performed prior to vaccination and approximately 7 days after each study vaccination. Results will be graded using the FDA Toxicity Grading Scale for Healthy Adult and Adolescent Volunteers Enrolled in Preventative Vaccine Clinical Trials [4] and recorded by severity as mild/grade 1, moderate/grade 2, severe/grade 3, and potentially life threatening/grade 4, in addition to low (below normal range) and high (above normal range).

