## 9. SAFETY EVALUATION

Summaries and analyses of safety data will be presented for the safety analysis population.

Solicited non serious AEs will be collected from the time of each vaccination until 7 days after. Solicited AEs will be summarized by severity for each day post each vaccination and as the maximum severity over all 8 days. Additionally, solicited AEs will be analyzed using standard techniques, such as 95% CIs (using the Clopper-Pearson method), to summarize the proportion of participants reporting each symptom, any local (vaccination site) symptom, and any systemic symptom.

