### 9.3.1. Solicited Events and Symptoms

Systemic solicited AEs were collected pre-vaccination, and systemic and local solicited AEs were collected 30 minutes post-vaccination and then daily for 7 days after each vaccination. Solicited local events include erythema (redness), induration (hardness)/edema (swelling), pain, and tenderness. Solicited systemic events include fever, chills (feverishness), fatigue (tiredness), malaise (general unwell feeling), myalgia (body aches/muscular pain exclusive of the injection site), arthralgia (joint pain exclusive for the injection site), headache, nausea, and diarrhea. Solicited events were graded on a scale of none (absent), mild, moderate, and severe. Measurement values for erythema and induration (hardness)/edema (swelling) were collected and graded based on the FDA Toxicity Grading Scale for Healthy Adult and Adolescent Volunteers Enrolled in Preventative Vaccine Clinical Trials [[4](#)].

Solicited AEs are summarized by severity pre-vaccination (systemic solicited AEs only), post-vaccination, and each day post-study vaccination (Days 1-8). Solicited AEs are also summarized by the maximum severity over all post-vaccination measurements. The proportions of participants reporting each symptom, any local symptom, any systemic symptom, and any symptom are summarized by vaccination arm separately for each dose and both doses combined (where applicable). For each event the denominator is the number of participants with non-missing data for the event.

The following summaries for solicited adverse events are presented by maximum severity, vaccination (each dose separately and both doses combined, where applicable), and vaccination arm:

- Number and percentage of participants experiencing solicited events by symptom and maximum severity, for any symptom, local symptoms, and systemic symptoms (beginning with [Table 222](#) and ending with [Table 230](#))
- Number and percentage of participants experiencing any solicited event, any systemic event, any local symptom, and each symptom, by day and severity, for each vaccination (starting with [Table 231](#) and ending with [Table 250](#))

- Duration of solicited symptoms summarized by mean, standard deviation, median, minimum, and maximum by symptom, dose, and vaccination arm ([Table 251](#), [Table 252](#), [Table 253](#), [Table 254](#), and [Table 255](#))

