## 9.7. Vital Signs and Physical Evaluations

Vital signs including oral temperature, pulse, and systolic and diastolic blood pressure will be taken at each in-clinic visit. Vital signs assessed on Day 1 prior to the first study vaccination will be considered as baseline. Vital signs will be graded using the FDA Toxicity Grading Scale for Healthy Adult and Adolescent Volunteers Enrolled in Preventative Vaccine Clinical Trials [4] and recorded by severity as mild/grade 1, moderate/grade 2, severe/grade 3, and potentially life threatening/grade 4. Results will be tabulated by time point, severity, and vaccination arm for each vital sign and all vital signs combined ([Table 332](#), [Table 333](#), [Table 334](#), [Table 335](#), and [Table 336](#)).

Individual participant listings of vital signs will be presented ([Listing 14](#)).

A targeted physical examination may be performed, if indicated, based on review of interim medical history. Height and weight will be collected on Day 1 prior to the first study vaccination to calculate BMI, which will be presented with continuous demographics ([Table 42](#), [Table 43](#), [Table 44](#), [Table 45](#), and [Table 46](#)). Individual participant listings of physical exam findings will be presented ([Listing 15](#)).

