## 14.3 Safety Data

### 14.3.1 Displays of Adverse Events

**Table 212: Overall Summary of Adverse Events by Vaccination Arm – COVID-19 Vaccination Naïve, 18-60 years of age, Groups 1 and 3A**

Participants a with		Group 1: $5 \times 10^{10}$ vp ChAd-S/30 µg SAM-S (N=X)		Group 3A: 30 µg SAM-S/30 µg SAM-S (N=X)		All Participants (N=X)	
Category 1	Category 2	n	%	n	%	n	%
At least one local solicited adverse event	NA						
At least one systemic solicited adverse event	NA						
At least one unsolicited adverse event	NA						
At least one related unsolicited adverse event	Any Grade						
	Mild (Grade 1)						
	Moderate (Grade 2)						
	Severe (Grade 3)						
At least one severe (Grade 3) unsolicited adverse event	Any relationship						
Related	Related						
Unrelated	Unrelated						
At least one serious adverse event b	Any relationship						
	Related						
At least one adverse event leading to early termination c	NA						
At least one adverse event leading to treatment discontinuation	NA						
Any laboratory Adverse Event	NA						

Participants a with		Group 1: $5 \times 10^{10}$ vp ChAd-S/30 µg SAM-S (N=X)		Group 3A: 30 µg SAM-S/30 µg SAM-S (N=X)		All Participants (N=X)	
Category 1	Category 2	n	%	n	%	n	%
Any Vital Signs Adverse Event	NA						
At least one medically attended adverse event	NA						
At least one new onset chronic medical condition	NA						

N = Number of participants in the Safety Population  
aParticipants are counted once for each category regardless of the number of events.  
bA listing of Serious Adverse Events is included in [Table 307](#).  
cAs reported on the Adverse Event eCRF.

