Symptom	Severity	n	%	n	%	n	%	n	%	n	%	n	%	n	%	n	%	n	%	n	%		
Nausea	None																						
	Mild																						
	Moderate																						
	Severe																						
	Not Reported																						
Any Local Symptom	None																						
	Mild																						
	Moderate																						
	Severe																						
	Not Reported																						
Erythema	None																						
	Mild																						
	Moderate																						
	Severe																						
	Not Reported																						
Erythema Measurement (mm)	None																						
	Mild																						
	Moderate																						
	Severe																						
	Not Reported																						
Edema/Induration	None																						
	Mild																						
	Moderate																						
	Severe																						
	Not Reported																						

		Pre-Dose ( N=X )		Post-Dose (N=X)		Day 1 (N=X)		Day 2 (N=X)		Day 3 (N=X)		Day 4 (N=X)		Day 5 (N=X)		Day 6 (N=X)		Day 7 (N=X)		Day 8+  (N=X)		Any Post-Dose 	
Symptom	Severity	n	%	n	%	n	%	n	%	n	%	n	%	n	%	n	%	n	%	n	%		
Edema/Induration Measurement (mm)	None																						
	Mild																						
	Moderate																						
	Severe																						
	Not Reported																						
Pain	None																						
	Mild																						
	Moderate																						
	Severe																						
	Not Reported																						
Tenderness	None																						
	Mild																						
	Moderate																						
	Severe																						
	Not Reported																						

Severity is the maximum severity reported post dosing for each participant for each day.

 Day 8+ includes the maximum severity of each symptom reported on or after Day 8 (includes ongoing symptoms)

Indicates how many participants had “None”, “Mild”, “Moderate”, “Severe”, or “Not Reported” as their maximum severity for any day. A participant may be counted in more than one of these categories.

Tables with similar format:

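### The laboratory, vital-sign and unsolicited-event summary shells have no Grade 4 category although the SAP grades to Grade 4, and the solicited maximum-severity shells omit the named exact CIs and, as read, the Tenderness row

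*SAP*

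**What the plan says.** Section 8.1 makes the Section 9 safety analyses the primary endpoints.

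**Grading in the text.** Section 4.5 (Clinical Laboratory Assessments) has laboratory results "recorded by severity as mild/grade 1, moderate/grade 2, severe/grade 3, and potentially life threatening/grade 4", with a low or high direction added. Section 9.7 grades vital signs as "mild/grade 1, moderate/grade 2, severe/grade 3, and potentially life threatening/grade 4" and says they are tabulated by severity. Appendix 1, under 12.2.2, grades all adverse events and SAEs on the same cited FDA toxicity scale.

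**Severity in the shells.** In Table 312 the highest category is "Severe/ Grade 3 (High", and the next column is Missing. Table 212 has a row "At least one severe (Grade 3) unsolicited adverse event" and none above it. Section 9.3.2 promises a listing of non-serious events of at least moderate severity, but the shell is titled "Listing of Non-Serious, Unsolicited, Moderate or Severe Adverse Events".

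**Solicited events.** Section 9 says these will be analysed with standard techniques, "such as 95% CIs (using the Clopper-Pearson method), to summarize the proportion of participants reporting each symptom", and likewise any local and any systemic symptom. Section 9.3.1 states: "Solicited local events include erythema (redness), induration (hardness)/edema (swelling), pain, and tenderness".

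**The concern.** A shell is what the programmer follows. If the text allows four grades and the table has three, a Grade 4 result must be put under Grade 3, or left out so that the row no longer adds up to its N. Either way, the summary of the primary endpoint misstates the worst category. The row meant to give each participant's maximum severity after baseline cannot show the maximum that the text allows.

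The missing intervals matter for a different reason. With arms of 3 to 12 participants, 0% printed alone can be read as evidence of safety when the data hardly limit the true rate. Section 9 names the interval that would prevent this reading, and the shells do not carry it.

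**Working it through.** **1. Text against shells: grades.**

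| Data | Scale in the text | Shells | Highest category shown |
|---|---|---|---|
| Chemistry | Grades 1-4, low/high (4.5) | 312; 313-318 same format | Grade 3 low/high, then Missing |
| Hematology | Grades 1-4, low/high (4.5) | 325; 326-328 same format | Grade 3 low/high, then Missing |
| Vital signs | Grades 1-4 (9.7) | 332; 333-336 same format | Severe, then Missing |
| Unsolicited events | Same cited scale (Appendix 1, 12.2.2) | 212-216; 256-306 | Severe (Grade 3) |
| Solicited events | None to severe (9.3.1) | 222-250 | Severe, which matches the text |

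No implementation note under Tables 312, 325 or 332 adds a fourth grade. As an illustration, take an arm of 10 with nine participants without abnormality and one at Grade 4. The Table 312 columns then add up to 9 of 10, or the tenth participant is entered as Grade 3.

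The unsolicited tables differ among themselves. Tables 256-272 have only Mild, Moderate and Severe rows, so a Grade 4 event has no cell at all. Tables 273-289 have a total column and Tables 290-306 an any-incidence column; a Grade 4 event would be counted there but under no severity.

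**2. Text against shells: solicited events.** Section 9 names the interval for each symptom, any local symptom and any systemic symptom. Table 222, with Tables 223-230 in the same format, has n and % only. This is not a general convention of the shells: the neutralization and ICS shells (Tables 72 and 202) print 95% CIs. Table 222 as read ends at Pain. Tables 231 and 251 do have Tenderness rows.

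**3. The plan's own safety arithmetic.** The SAP states no figure for this point, so the nearest check is Table 4, using Pr(0 events) = (1 − p)^n.
- n = 7, p = 20%: 0.8^7 = 20.97%, so Pr(1+) = 79.03%, against 79.0% stated.
- n = 10, p = 10%: 0.9^10 = 34.87%, against 34.9% stated.

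All 16 rows (48 probabilities) reproduce to rounding. The arithmetic is sound, and the fault is confined to the shells.

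**4. What the missing intervals would show.** For x events in n participants, the two-sided 95% Clopper-Pearson limits are the 0.025 quantile of Beta(x, n − x + 1) and the 0.975 quantile of Beta(x + 1, n − x). For x = 0 the lower limit is 0 and the upper limit reduces to 1 − 0.025^(1/n). The group sizes come from SAP Table 2.

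| n | 0 events: upper limit | 1 event: interval |
|---|---|---|
| 3 | 70.8% | 0.8% to 90.6% |
| 4 | 60.2% | 0.6% to 80.6% |
| 7 | 41.0% | 0.4% to 57.9% |
| 8 | 36.9% | 0.3% to 52.7% |
| 10 | 30.8% | 0.3% to 44.5% |
| 12 | 26.5% | 0.2% to 38.5% |

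**The case against.** The strongest reply is that nothing disappears from the report. Tables 310 and 311 list abnormal laboratory results with their severity. Listings 12-14 give all laboratory and vital-sign results, Listing 11 gives all unsolicited events, and Table 307 gives the SAEs. With at most 12 participants in an arm, these listings are easy to read. This stands, and it limits the point. A reader might infer that a Grade 4 result would be lost, and that one such result is 8% (1/12) to 33% (1/3) of an arm. What is missing is its cell in the summary tables, not the record of it.

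A reader might also infer that dose escalation would turn on these tables. The documents do not support that. The Preface ties the shells to the final analyses, while Sections 4.1 and 6.2 leave escalation to the Study Steering Committee, with the DSMB as needed, on separate safety reviews.

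For unsolicited events the case is less direct. Sections 4.5 and 9.7 state four grades for laboratory values and vital signs only; for adverse events the link is the toxicity scale cited in Appendix 1. If the protocol, which is not at hand, grades events as mild, moderate or severe only, then these shells and the title of Table 308 are consistent.

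On intervals, the wording in Section 9 is loose and covers solicited proportions only. Their absence from Tables 212-216 is therefore not a contradiction.

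Finally, Table 231 might be read as breaking the maximum-severity rule of Section 9.3.1, because its Any Post-Dose column carries the note "A participant may be counted in more than one of these categories". It does not. Section 9.3.1 plans two displays, Tables 222-230 deliver the maximum-severity one, and the multiple counting is disclosed. The column can mislead, since one clear day places a participant under None, but that is a matter of labelling.

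**Conclusion.** The shells are wrong as written, and the correction is a should-fix.

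- **Laboratory and vital signs:** a direct conflict between text and shells in Tables 312-318, 325-328 and 332-336. It needs no assumption beyond the SAP's own wording.
- **Unsolicited events:** the same gap in Tables 212-216 and 256-306, with the title of Table 308 narrower than Section 9.3.2. This assumes that the scale cited in Appendix 1 applies to adverse events with all four grades.
- **Solicited events:** the intervals named in Section 9 are missing from Tables 222-230. Their size is far from negligible: for zero events the upper limit runs from 26.5% (n = 12) to 70.8% (n = 3).
- **Tenderness:** absent from Table 222 as read. The Fever row there carries a footnote mark with no matching footnote, so the foot of the table may be incomplete and should be checked against the source. Section 9.3.1 requires the symptom in either case.

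The layout of the laboratory bar graphs (Figures 664-668) is not shown and could not be checked. The solicited shells rightly stop at Severe.

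**What to change.** 1. Add a category for potentially life-threatening (Grade 4) results to Tables 312-318 and 325-328, split into low and high, and to Tables 332-336. Apply it to the by-visit rows and to the row for maximum severity after baseline.
2. Add the same category to the unsolicited tables (212-216 and 256-306), in line with the scale cited in Appendix 1. If the protocol grades adverse events on three levels, say so in the SAP instead.
3. Retitle Table 308 so that it covers every grade from moderate upwards, as Section 9.3.2 says.
4. Add 95% Clopper-Pearson intervals to Tables 222-230 for each symptom, any local symptom and any systemic symptom, and add a Tenderness row.
5. Optional: in Tables 231-250, make Any Post-Dose one maximum severity per participant, or relabel the column so that the multiple counting is plain from its heading.

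The cost is shell edits and somewhat wider tables. No new data are needed, and the interval method is already named in Section 9.

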## Implementation Note:

The vaccination arms receiving one dose will be shown at Days 1 and 8 only. Groups 1 and 3A will be shown at Days 1, 8, 29, and 36. Groups 3B and 4 will be shown at Days 1, 8, 85, and 92). All vaccination arms will be shown in the Max Severity Post-Baseline row.

Tables with similar format:

**Table 313: Laboratory Results by Parameter, Maximum Severity, Study Day, and Vaccination Arm – Alanine Aminotransferase**

**Table 314: Laboratory Results by Parameter, Maximum Severity, Study Day, and Vaccination Arm – Aspartate Aminotransferase**

**Table 315: Laboratory Results by Parameter, Maximum Severity, Study Day, and Vaccination Arm – Alkaline Phosphatase**

**Table 316: Laboratory Results by Parameter, Maximum Severity, Study Day, and Vaccination Arm – Total Bilirubin**

**Table 317: Laboratory Results by Parameter, Maximum Severity, Study Day, and Vaccination Arm – Creatine Kinase**

**Table 318: Laboratory Results by Parameter, Maximum Severity, Study Day, and Vaccination Arm – Creatinine**

**Table 319: Laboratory Summary Statistics by Parameter, Time Point, and Vaccination Arm – Alanine Aminotransferase**

Time Point	Vaccination Arm	N	Mean	Standard Deviation	Median	Min, Max
Baseline	Group 1: $5 \times 10^{10}$ vp ChAd/ 30 $\mu$ g SAM-S	x	xx.x	xx.x	xx.x	xx.x, xx.x
	Group 3A: 30 $\mu$ g SAM-S/ 30 $\mu$ g SAM-S					
	Group 3B: 30 $\mu$ g SAM-S/ 3 $\mu$ g SAM-S					
	Group 4: 10 $\mu$ g SAM-S-TCE/ 3 $\mu$ g SAM-S-TCE					
	Group 5: 3 $\mu$ g SAM-S-TCE					
	Group 6: 6 $\mu$ g SAM-S-TCE					
	Group 9: 3 $\mu$ g SAM-S-TCE					
	Group 10: 6 $\mu$ g SAM-S-TCE					
	Group 11: 10 $\mu$ g SAM-S-TCE					
	Group 13: $5 \times 10^{10}$ vp ChAd-S-TCE					
	Group 14: $1 \times 10^{11}$ vp ChAd-S-TCE					
	Group 15: $5 \times 10^{11}$ vp ChAd-S-TCE					
All Participants						
Day 8	...					
Day 8, Change from Baseline	...					
Day 29 (pre-dose 2 for Groups 1 and 3A)	...					
Day 29, Change from Baseline						
Day 36 (8 days post-dose 2 for Groups 3A and 4)						
Day 36, Change from Baseline						
Day 85 (pre-dose 2 for Groups 3B and 4)						
Day 85, Change from Baseline						
Day 92 (8 days post-dose 2 for Groups 3B and 4)						
Day 92, Change from Baseline						

Note: N = Number of participants in safety population

